Participants will receive automatic email (and text) reminders from the study management system if they have not completed the questionnaires or not accessed *DKIN: Teen.* The research team will also call a parent or send a check-in email to a parent if there is no response following the automatic reminder. Incentives for completing the pretest questionnaires and for completing the posttest questionnaires will be physically mailed to parent-adolescent pairs using the address provided on their study forms. At the end of the study, responses on the online questionnaires will be downloaded from the online data collection system and saved on a secure, password-protected network in preparation for statistical analyses.

Measures.

Adolescents

Knowledge. This measure has been created for the purposes of this study. Adolescents will respond to 27 questions that assess their factual knowledge about clinical research (e.g., "What is a clinical trial?"). Questions are in multiple choice format (some questions have multiple correct answers), and the total score could range from 0-53 correct. Higher scores indicate more knowledge about clinical research.

Attitudes about clinical trials. This measure was originally adapted from Madsen and colleagues (2002) and used in Parker et al (2022). The items are slightly adapted. Adolescents will be asked to respond to 6 questions that assess their positive attitudes about clinical trials (e.g., How do you feel about teens participating in clinical trials?; 1=Not good at all; 2=Not very good; 3=Not sure; 4=Good; 5=Very good; $\alpha = 0.83$). Responses will be averaged and the minimum scale score is 1 and the maximum scale score is 5. Higher scores indicate more positive attitudes toward clinical trials.

Beliefs about clinical trials. Adolescents will be asked to respond to 5 questions about their beliefs about pediatric clinical research (e.g., I believe that clinical trials can help teens; 1=Strongly disagree; 2=Disagree; 3=Unsure; 4=Agree; 5=Strongly agree; $\alpha = 0.78$; Parker et al., 2022). Responses will be averaged and the minimum scale score is 1 and the maximum scale score is 5. Higher scores indicate more positive beliefs about clinical trials.

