Procedural fears. Adolescents will be asked to respond to 4 questions related to their perceptions of fear or anxiety about different types of medical procedures, including getting a needle in the arm, injection in the leg, getting a scan, and taking new medicine, on a 5-point Likert scale (1 = Not at all afraid or anxious, 2 = Somewhat afraid or anxious, 3 = Moderately afraid or anxious, 4 = Very afraid or anxious, 5 = Extremely afraid or anxious). Responses will be averaged and the minimum scale score is 1 and the maximum scale score is 5. Higher scores indicate more fear about procedures. The original measure has strong reliability and validity (Kowalsky et al., 2014).

Likelihood of participation in clinical trials. Adolescents will be asked to respond to one question about the likelihood of participating in a clinical trial (i.e., "If you were asked to be in a clinical trial, how likely would you be to participate?") using a 5-point Likert scale (1 = Not likely at all; 2 = Not very likely; 3 = Not sure; 4 = Likely; 5 = Very likely). Responses will be averaged and the minimum scale score is 1 and the maximum scale score is 5. Higher scores indicate greater likelihood of participation in a clinical trial.

Likelihood of fear preventing participation in clinical trials. Adolescents will be asked to respond to one question about the likelihood of their fear preventing them from participating in a clinical trial (i.e., "How likely is it that your fearful or anxious feelings could stop you from participating in a clinical trial in the future?") using a 5-point Likert scale (1 = Not likely; 2 = Somewhat likely; 3 = Moderately likely; 4 = Very likely; 5 = Extremely likely). Responses will be averaged and the minimum scale score is 1 and the maximum scale score is 5. Higher scores indicate greater likelihood of fear preventing participation in a clinical trial.

Familiarity with clinical trials. Adolescents will be asked to respond to one question about their familiarity with clinical trials ["How much do you know about pediatric clinical trials (research studies with children under 18)?"; 1 = I don't know anything; 2 = I know a little about them; 3 = I know some things about them; 4 = I know a lot about them; 5 = I know all there is to know about them]. Responses will be averaged and the minimum scale score is 1 and the maximum scale score is 5. Higher scores indicate greater familiarity with pediatric clinical trials.

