Willingness to participate in a clinical trial. Adolescents will review five research protocols related to a fictitious disease ('meditis') and respond to a question about their willingness to participate in each research study (e.g., If you had meditis, would you agree to enroll in this study?; 1 = Definitely not to 7 = Definitely yes). Responses will be averaged across the five protocols and the minimum scale score is 1 and the maximum scale score is 7. Higher scores indicate greater willingness to participate in the research studies. This measure was adapted from Brody and colleagues (2005).

Quality of parent-adolescent communication. Adolescents will be asked to respond to 8 questions related to their perceptions of their relationship quality and communication with their parents (e.g., "My parent gives me good advice."; "When talking to my parent, he/she tries to understand my point of view."; 1 = Strongly disagree; 2 = Disagree; 3 = Agree; 4 = Strongly agree). Responses will be averaged and the minimum scale score is 1 and the maximum scale score is 4. Higher scores indicate more positive perceptions of relationship quality. This measure has strong reliability (Mallett et al., 2011).

Parents

Attitudes about clinical trials. Parents will be asked to respond to 6 questions that assess their positive attitudes about clinical trials (e.g., How do you feel about teens participating in clinical trials?; 1=Not good at all; 2=Not very good; 3=Not sure; 4=Good; 5=Very good). Responses will be averaged and the minimum scale score is 1 and the maximum scale score is 5. Higher scores indicate more positive attitudes toward clinical trials. This measure was adapted from Madsen and colleagues (2002) and used in Parker et al (2022).

Beliefs about clinical trials. Parents will be asked to respond to 5 questions about their beliefs about pediatric clinical research (e.g., I believe that clinical trials can help teens; 1=Strongly disagree; 2=Disagree; 3=Unsure; 4=Agree; 5=Strongly agree). Responses will be averaged and the minimum scale score is 1 and the maximum scale score is 5. Higher scores indicate more positive beliefs about clinical trials. This measure was adapted from Parker et al (2022).

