Consumer Satisfaction Questionnaire for Parents (*CSQ-P*) will assess parents' satisfaction with the Parent-Teen Shared Decision-Making section of *DKIN: Teen* in terms of (1) content, (2) format, and (3) usability. Participants will rate each item on a 5-point Likert scale (1 = Strongly disagree; 5 = Strongly agree). Parents will also be asked to provide open-ended feedback. Finally, parents will complete 12 items related to the acceptability (AIM), appropriateness (IAM), and feasibility (FIM) of the Shared Decision-Making section, using a 5-point Likert scale (1 = Completely disagree; 5 = Completely agree; Weiner et al., 2017).

Statistical Analysis Plan

Data will be analyzed using SAS 9.4.

Preliminary analyses. Preliminary analysis will include a test of equivalency between groups on demographic background characteristics using chi-squared analyses for categorical variables and t-tests for continuous variables. Psychometric analyses will be conducted to examine the reliability, validity, and distributions of key variables. Handling variables with poor reliability or validity will include modification or elimination of such variables from the analysis data sets. Variables with noticeably skewed distributions will be transformed or categorized to reduce the impact of non-normality on subsequent analyses. Descriptive statistics will also be conducted to examine the distributions, correlations, means, and standard deviations of the adolescent and parent outcome variables (listed in the Measures section).

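### The rule for skewed variables lets outcomes be categorised, which usually costs power, takes the result off the Measures scale, and is not needed to deal with skew

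*Combined protocol and SAP*

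**What the plan says.** The SAP, under Preliminary analyses, begins with a look at distributions: "Psychometric analyses will be conducted to examine the reliability, validity, and distributions of key variables". The rule at issue follows: "Variables with noticeably skewed distributions will be transformed or categorized to reduce the impact of non-normality on subsequent analyses". The next sentence turns to the outcomes themselves: "Descriptive statistics will also be conducted to examine the distributions, correlations, means, and standard deviations of the adolescent and parent outcome variables". Nothing exempts outcomes or their pre-test scores, so on the natural reading they are covered. The rule gives no skewness threshold, no basis for choosing between its two branches, no cut-points or number of categories, and no model for a categorised outcome.

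Main analyses then plans a multiple regression of each post-test outcome on condition and its pre-test score. It promises adjusted post-test means, and an effect size equal to the contrast divided by the sample standard deviation of the outcome.

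Measures defines four kinds of score:
- knowledge, where "the total score could range from 0-53 correct";
- most rating scales and the single items: "Responses will be averaged and the minimum scale score is 1 and the maximum scale score is 5";
- willingness: "Responses will be averaged across the five protocols and the minimum scale score is 1 and the maximum scale score is 7";
- communication quality: "Responses will be averaged and the minimum scale score is 1 and the maximum scale score is 4".

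**The concern.** The two branches are treated as interchangeable, and they are not. A transformation keeps the ordering and nearly all the information in a score. Categorising discards the differences within each category, which usually weakens the comparison of arms. All the outcomes are bounded and some are single 5-point items, so floor or ceiling skew is an ordinary possibility, although the documents give no data on it.

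Two things are at stake for an outcome that is skewed and then categorised. Its test would usually be weaker than the regression already planned. Its adjusted mean and effect size would also no longer refer to the score defined in Measures. If the form were binary and the model logistic, the result would be an odds ratio, and neither planned summary would exist. The stated reason for the rule is non-normality, so the remaining question is whether non-normality harms the planned regression enough to justify this.

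**Working it through.** The plan gives no sample size, power, alpha, effect size or skewness, so there is no figure to reproduce. Everything below is a simulation under stated assumptions.

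**Inputs from the documents.** 1:1 allocation; regression of post-test on condition and pre-test; score ranges 0-53, 1-7, 1-5 and 1-4.

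**Assumptions.** 100 per arm; two-sided 5% test; items cut from a latent normal variable; pre/post latent correlation 0.6; latent shift 0.35-0.70, set so that raw-score power is 72-78%; shifts in both directions. Raw and log forms: linear regression with the pre-test in the same form. Three categories: tertile cuts scored 0-2, linear regression; where more than two thirds sit at the floor, the floor plus a cut at the median of the rest. Median split: logistic regression on the split post-test and split pre-test.

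**Step 1: power at moderate skew (0.87-0.97), upward shift.** Relative efficiency = [(z_form + 1.96) / (z_raw + 1.96)]², where z is the normal quantile of the power.

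| Score | Raw | Log | Three categories | Split | Efficiency, three | Efficiency, split |
|---|---|---|---|---|---|---|
| 1-5, one item | 0.730 | 0.733 | 0.671 | 0.574 | 0.87 | 0.70 |
| 1-5, four items | 0.741 | 0.750 | 0.639 | 0.529 | 0.79 | 0.61 |
| 1-7, five items | 0.750 | 0.755 | 0.638 | 0.512 | 0.77 | 0.57 |
| 1-4, eight items | 0.778 | 0.789 | 0.668 | 0.537 | 0.77 | 0.57 |
| 0-53 | 0.746 | 0.724 | 0.630 | 0.508 | 0.76 | 0.57 |

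For 0-53, z is 0.662 (raw), 0.332 (three) and 0.020 (split). This gives (2.292/2.622)² = 0.76 and (1.980/2.622)² = 0.57. Over both shift directions the ranges are 0.76-0.95 for three categories, 0.57-0.81 for the split and 0.95-1.06 for log.

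**Step 2: strong skew (1.4-1.9), where the rule is more likely to be triggered.**
- Multi-item and knowledge scores: three categories 0.80-0.97 (3-20% lost); split 0.62-0.74 (26-38% lost).
- Single item: three categories 0.99-1.02 (no loss); split 0.88-0.98 (2-12% lost).
- Log: 1.04-1.12 (a gain of 4-12%).

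In power terms, take raw power of 75% (z = 0.674, so z + 1.96 = 2.634) and multiply 2.634 by the square root of the efficiency. Efficiency 0.97 gives 2.595 and power 74%; 0.80 gives 2.356 and 65%; 0.74 gives 2.266 and 62%; 0.62 gives 2.074 and 55%.

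**Step 3: is categorising needed?** With no true effect, raw-score regression rejected 4.5-5.4% of the time over 10 settings (Monte Carlo standard error 0.3 points), covering all four score ranges.

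**Step 4: sensitivity.** With 50 per arm, or correlation 0.4 or 0.8, efficiency was 0.65-1.04 for three categories and 0.45-0.98 for the split, and raw type I error was 4.1-5.9%.

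**Step 5: a second simulation with different distributions** (64, 100 or 150 per arm; raw power 62-71%). For the multi-item scores (skewness about 1.4-1.5 in size), the powers convert by the same formula to 0.81-0.90 for tertile scores and 0.58-0.67 for the split. For 64 per arm and right skew, power fell from 0.666 to 0.622, and (2.271/2.389)² = 0.90. A single item with skewness about 1.1 did lose power under tertile cuts, for example 0.666 to 0.492. Half the control answers sat in the lowest category there, so the cuts mostly reduce to two levels. The absence of loss for a single item in step 2 therefore depends on how the cuts are placed.

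**Step 6: reporting.** Linear regression on a 0-2 score gives an adjusted mean and a contrast divided by a standard deviation, both in category units. Logistic regression on a split gives an odds ratio. A transformed score also leaves the Measures units unless it is back-transformed.

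**The case against.** The strongest reply is that the harm needs three conditions: an outcome must be noticeably skewed, the categorise branch must be taken, and the cut must be coarse. The same sentence offers transformation, which costs almost nothing. The median split is an illustration and not something the plan specifies, and the largest losses arise at skewness just below 1, where the rule is less likely to apply. All of this stands. It limits the point to a conditional one and is why the strong-skew figures are the ones to quote. It does not remove the point, because nothing in the plan steers outcomes away from the costlier branch.

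A second reply is that Main analyses does not say its means and effect sizes must be on the Measures scale, and that transformation also moves them off it. This also stands. A reader might infer that a categorised outcome could not be reported as planned at all, or could not be set beside the other outcomes. The documents do not support that: no logistic model is named, and a scored three-level form analysed by the planned regression still yields both summaries. In cells re-run as a check, its standardised effect was within 0.03 of the raw-score effect.

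A reader might also infer that the rule lets the sponsor pick the most favourable form and so inflates type I error. The plan does not propose this. The step sits under Preliminary analyses and is triggered by the distribution; a choice made on skew alone, blind to condition, does not raise type I error. Blinding of that choice is not stated, but the only related text, "At the end of the study, responses on the online questionnaires will be downloaded from the online data collection system", does not say who sees condition. That is a gap in wording and not evidence of selection.

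**Conclusion.** The point holds as a minor, conditional improvement to a stated rule. If an outcome is categorised, its test usually loses power. At strong skew the illustrative loss is about 3-20% of efficiency with three categories, and about 26-38% with a median split, for multi-item and knowledge scores; a single item lost nothing with three well-placed categories. The planned adjusted mean and effect size move to category units, or are unavailable under a logistic model. Raw-score regression held its error rate near 5% in the settings simulated, so the stated purpose does not require categorising.

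The direction rests on simulations of bounded scores and could reverse where answers pile up at one end and the cut falls there. The size rests on assumed sample size, effect, correlation, skewness and cuts, none of which the documents give; the sensitivity ranges are wide. Nothing here shows that any outcome will be skewed or categorised.

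**What to change.** For outcomes and their pre-test scores, replace the rule with: *Outcomes are not categorised in the main regression; each is analysed on the scale defined in Measures. Any transformed (or, for single items, proportional-odds) analysis is specified before group comparisons are seen and reported as a sensitivity analysis.*

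If the sponsor prefers to keep transformation in the main analysis, it is enough to remove the option to categorise outcomes and to fix the transformation rule in advance, blind to condition. The present sentence may stay for non-outcome variables such as time spent on the website.

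The cost is SAP wording only, with no extra data. Under the first option, a small efficiency gain from log transformation of strongly skewed outcomes (4-12% in the simulation) may be given up in the main analysis.

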Study Protocol and Statistical Analysis Plan

Title of Study: Web-based Resource for Children and Adolescents About Clinical Research ClinicalTrial.gov Identifier: NCT05714943 Principal Investigators: [name]; [name] Date of Document: 01/24/2023

	Page number
Study Protocol	3
Objectives	3
Design	3
Methods	4
Statistical Analysis Plan	10

Study Protocol

Objectives:

Clinical trials with pediatric populations are needed in order to ensure the treatments are tested with and work for children and adolescents. However, there are a number of barriers to recruitment and enrollment of children and adolescents. *DigiKnowIt News: Teen (DKIN: Teen)* is an interactive educational website designed to educate adolescents (aged 12 to 17) about pediatric clinical research and equip them with information to make informed decisions about participation. The main objective of the study is to test the effectiveness of *DKIN: Teen* related to factors that could influence participation in pediatric clinical trials. This study will examine if *DKIN: Teen* increases adolescents' knowledge about clinical trials, adolescents' and parents' positive attitudes and beliefs towards clinical trials, adolescents' self-efficacy about the decision to participate in a clinical trial, adolescents' and parents' communication quality, as well as reduce adolescents' fears associated with research participation.

Design:

The study is a parallel group randomized controlled trial with a 1:1 allocation ratio and superiority framework to test the efficacy of *DKIN: Teen* for improving factors related to clinical trial participation among parent-adolescent pairs. The randomized controlled trial will be conducted online at two time points: 1) baseline/pre-test and 2) post-test (one week after pre-test). The study questionnaires will be programmed into an online data collection system and the intervention itself is also completed online.

Participants will be randomized, stratifying based upon gender (boy; girl; non-binary), race/ethnicity (white and not Hispanic/Latino; nonwhite and/or Hispanic/Latino), and health status (health;/chronic illness), to one of two conditions: 1) intervention (pairs will receive access to *DKIN: Teen* right away) or 2) wait-list control (pairs will not have access to the intervention between pre-test and post-test assessments; after completing the post-test questionnaire, pairs will be given the option to review *DKIN: Teen*).

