Participants are randomized and enrolled based on: 1) time study forms (e.g., consent) were completed, 2) confirmation of email addresses, and, 3) their reported demographics collected in the eligibility screener questions (described below in the Sample and Recruitment section). One of the leading investigators will generate the allocation sequences using a random number generator in Excel. After eligibility is determined, the other leading investigator will assign participants to condition (either intervention or wait-list control) according to those sequences and then enroll participants in the study. The allocation sequence will be stored in a folder on a secure, password-protected server and will only be accessible by the leading investigator who created the sequence. All participants will be assigned a unique ID number that will be associated with their data in place of a name.

Methods:

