Sample and Recruitment. Parent-adolescent (ages between 12 and 17 years) pairs will be recruited for the study. To be eligible to participate in the study, the following criteria must be met: a) adult participant is a parent or legal guardian of adolescent participant; (b) adolescent participant is 12-17 years of age; (c) parent-adolescent pair has access to a computer or tablet with internet connection; (d) ability to speak and read in English; and (e) no current or previous participation in a clinical trial after kindergarten. This study will investigate if the DKIN: Teen website improves attitudes and decision-making of adolescents who have not yet participated in a clinical trial and thus, excludes those who have already had the experience of being in a clinical trial. Parent-adolescent pairs will be recruited from across the United States. A study recruitment website will contain information about DKIN: Teen and the research study that interested parentadolescent pairs can review. Parent-adolescent pairs will also be recruited via flyers and with the help of consultants who have access to networks of pediatric groups and pediatric health organizations, as well as help from other health advocacy and parent groups. Study flyers will also be shared via email and social media (e.g., Facebook) and via PeachJar, a digital flyer service within school districts. Efforts will be made to ensure about equal samples of boys and girls as well as healthy adolescents and adolescents with varying chronic diseases/disorders between the intervention and wait-list control groups. The sample will represent diversity in ethnicity and race.

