Procedure. Interested parents and adolescents will visit the recruitment website to learn more about the study and respond to the study eligibility screening questions. In order to be eligible to participate in the study, a parent-adolescent pair must have access to computer or tablet with internet connection and English fluency. In addition, the adolescent participant must be within the ages of 12-17 and have NOT participated in a clinical trial. Parents will be asked to indicate their child's race, ethnicity, gender, and health status (healthy/have chronic illness) to assist in ensuring a diverse sample of participants. Parents will also be asked to indicate their own gender, race, and ethnicity. Parents will be notified onscreen immediately if their child is eligible to participate in the study, and if so, will be given access to online permission, consent, and assent forms. They will be instructed to review the forms together so they can decide about participation. Parents will complete an online consent form for their own participation and permission form for their child's participation and the adolescent will be asked to complete an online assent form. Interested participants who decide to complete the forms will be told that in an attempt to have a diverse sample, they may not be invited to participate. Parent-adolescent pairs can contact the research team about any questions they might have after they have reviewed and signed the forms.

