The permission, consent, and assent forms will describe the goals of the study, as well as the minor potential risks and the benefits of participation. Permission, consent, and assent forms will also state the participant may discontinue their participation at any time. Parents will be provided with the option to receive text messages related to their study participation in addition to receiving emails. Language in the adolescent assent will be appropriate for the age group in the study, in order to ensure that they understand all procedures. Potential parent-adolescent pairs will be provided with the contact information of the researchers and may contact them to ask any questions they may have about the study. Only parent-adolescent pairs with completed study forms will be permitted to participate in the study. Parent-adolescent pairs will read the permission, consent, and assent forms and provide online permission, consent and assent by typing their names into a text box, providing contact information, and clicking a button to indicate permission and consent (parent) or assent (adolescent), rather than providing us with a signed hard copy of the forms. They will have the option to download and/or print the forms to retain a copy for their files.

iRT project staff will determine whether or not the address the parent has provided for the pair in the informed consent forms is real using a Google map search. Eligible parent-adolescent pairs who have completed all study forms (parental consent and permission and adolescent assent) will be invited to participate by project staff members if there is space for them in the study depending on their demographic characteristics. Parents will receive a welcome email that will provide more information on the timeframe and tasks for the study. Approximately equal numbers of male/female adolescent participants and chronically ill/healthy adolescent participants will be randomly assigned to condition (*DKIN: Teen* OR wait-list control). The goal is to enroll a diverse sample of adolescents with respect to race and ethnicity.

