Main analyses. Multiple regression analyses will be used to investigate differences in outcomes (i.e., knowledge about clinical research, attitudes and beliefs towards pediatric clinical trials, self-efficacy in making decisions related to clinical trials, likelihood and willingness to participate in clinical trials, procedural fears, communication quality) using condition (intervention; wait-list control) as the independent variable of interest. A series of multiple regressions will be used to examine if using DKIN: Teen impacts the post-test knowledge, attitudes, efficacy, likelihood and willingness to participate, fears, and communication quality of participants. Pre-test scores for each outcome will be included as predictor variables; thus, outcome variable means will be reported as adjusted post-test scores. Demographic variables found to be non-equivalent between groups will be included as covariates in these models. The effect sizes will be calculated by dividing the appropriate contrast parameter by the sample standard deviation of the outcome. If unexpected results are obtained, then the process data recorded by the LMS (e.g., time spent on parts of DKIN: Teen website) and measures of satisfaction will be examined to investigate whether differing dosage or satisfaction levels can explain unexpected patterns of findings. Additional analyses will examine subpopulations and test age, gender, and health status (chronic illness/no illness) as potential moderators of the effectiveness of DKIN: Teen.

Analyses will be intention-to-treat, so that participants who do not adhere to the protocol are still included in the analysis in their assigned condition. Missing data will be handled in each

outcome analysis with an appropriate imputation method, and estimates and standard errors will be adjusted for imputations, if warranted.

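### The main models omit the randomisation stratification factors and pick covariates by baseline tests: a small power loss if those factors predict post-test beyond the pre-test score

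*Combined protocol and SAP*

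**What the plan says.** **Design.** "Participants will be randomized, stratifying based upon gender (boy; girl; non-binary), race/ethnicity" and health status, with 1:1 allocation. That is 3 × 2 × 2 = 12 strata. For the allocation itself, "One of the leading investigators will generate the allocation sequences using a random number generator in Excel"; blocks are not mentioned.

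**Balance aims.** Sample and Recruitment aims for about equal samples of "boys and girls as well as healthy adolescents and adolescents with varying chronic diseases/disorders between the intervention and wait-list control groups". Procedure says "Approximately equal numbers of male/female adolescent participants and chronically ill/healthy adolescent participants will be randomly assigned to condition". Neither passage names race/ethnicity, although Design stratifies on it.

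**Availability.** Under Procedure, the screener asks parents for their child's "race, ethnicity, gender, and health status (healthy/have chronic illness) to assist in ensuring a diverse sample of participants", so all three factors are known before assignment.

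**SAP, Preliminary analyses.** "Preliminary analysis will include a test of equivalency between groups on demographic background characteristics using chi-squared analyses for categorical variables", with t-tests for continuous ones. No significance threshold is given.

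**SAP, Main analyses.** The models are multiple regressions on condition. "Pre-test scores for each outcome will be included as predictor variables". Then: "Demographic variables found to be non-equivalent between groups will be included as covariates in these models". Gender and health status, with age, return only as moderators in additional analyses. Race/ethnicity does not return.

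**The concern.** The covariate rule works against the design. The better the stratification balances its factors, the less likely they are to fail a baseline test and so to be adjusted for. A demographic that does enter has been picked by chance imbalance, which says nothing about whether it predicts the outcome. The covariate set of every main model also stays unknown until baseline data have been tested, against a criterion the SAP does not define.

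What is at stake is power, and only if the factors predict post-test scores beyond the pre-test score already in each model. The form of the loss depends on how tightly assignment is balanced within strata, which the protocol does not specify:

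- **Case A, balanced strata.** The design has already removed the between-strata noise from the estimate, but the model still counts it as residual variance. The reported SE is too wide and the test is conservative.
- **Case B, no blocks.** The reported SE is about right, but the estimate is less precise than it could be.

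**Working it through.** **Inputs.** The documents give no sample size, alpha, power, effect size, SD, correlation or screening threshold, so there is no stated figure to reproduce. Everything below is assumed and shown over a range. Let R² be the share of post-test variance left after pre-test that the three factors explain, from 0 to 10%. With a pre/post correlation of 0.6, R² = 10% is 0.10 × (1 − 0.36) = 6.4% of total post-test variance; with 0.8 it is 0.10 × (1 − 0.64) = 3.6%.

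**Case A, analytic.** Two-sided alpha 0.05; noncentrality 2.802 (80% power when the SE is unadjusted and correct).

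- SE ratio, planned/adjusted = 1/√(1 − R²)
- Type I error, planned = 2 × (1 − Φ(1.96/√(1 − R²)))
- Power, planned = Φ((2.802 − 1.96)/√(1 − R²))
- Power, adjusted = Φ(2.802/√(1 − R²) − 1.96)

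Example at R² = 10%: 1/√0.90 = 1.054; 1.96 × 1.054 = 2.066, giving a type I error of 3.9%; planned power Φ(0.842 × 1.054) = Φ(0.888) = 81.3%; adjusted power Φ(2.954 − 1.96) = Φ(0.994) = 84.0%.

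| R² | SE too wide by | Type I error, planned | Power, planned | Power, adjusted |
|---|---|---|---|---|
| 2% | 1.0% | 4.8% | 80.2% | 80.8% |
| 5% | 2.6% | 4.4% | 80.6% | 82.0% |
| 10% | 5.4% | 3.9% | 81.3% | 84.0% |

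**Simulation of the planned rule.** Assumptions: 200 pairs; 48.5/48.5/3% boy/girl/non-binary; 40% nonwhite and/or Hispanic/Latino; 50% chronic illness; correlation 0.6; equal contribution of the three factors; six demographics screened at 0.05 (adolescent gender, race/ethnicity, health status and age; parent gender and race/ethnicity); 10,000 trials per cell. Ratios are planned/adjusted.

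| | R² 0 | 2% | 5% | 10% |
|---|---|---|---|---|
| *Blocks of 4:* true SD ratio | 0.999 | 1.001 | 1.001 | 1.005 |
| reported SE ratio | 1.000 | 1.010 | 1.026 | 1.054 |
| type I error, planned | 4.6% | 5.1% | 4.8% | 3.9% |
| power, planned | 79.4% | 79.6% | 79.3% | 80.5% |
| power, adjusted | 79.3% | 79.9% | 80.9% | 83.1% |
| *No blocks:* true SD ratio | 0.993 | 0.999 | 1.018 | 1.033 |
| reported SE ratio | 0.995 | 1.004 | 1.019 | 1.046 |
| type I error, planned | 5.2% | 5.0% | 5.0% | 5.0% |
| power, planned | 79.5% | 79.2% | 79.2% | 79.4% |
| power, adjusted | 78.8% | 79.5% | 80.7% | 82.6% |

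Monte Carlo standard errors are about 0.2 points for type I error, 0.4 for power and 0.003 for SD ratios. Adjusted type I error was 4.7–5.3% throughout.

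**In pairs, no blocks.** 200 × (SD ratio² − 1): at 5%, 200 × (1.018² − 1) ≈ 7; at 10%, 200 × (1.033² − 1) ≈ 13; at 2% about 0; at 0 about −3, so adjusting then costs slightly.

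**Break-even, no blocks.** Adjusting pays once R² exceeds about k/(N − 3), with k = 3–4 parameters: 3–4% at N = 100, 1.5–2% at N = 200 (3/197 to 4/197), 0.8–1% at N = 400.

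**How often the rule acts.** A stratification factor was selected in about 14% of trials without blocks and in at most 0.03% with blocks. Some covariate entered by chance in 24–25% and 10–11% of trials respectively; these two figures depend on parent and adolescent race/ethnicity being correlated. If they are independent, the figures are about 26% and 14.5%.

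**Sensitivity, no blocks, R² 10%.** The SE ratio is 1.041 at N = 100, 1.048 at N = 400, and 1.045 at N = 200 with a 0.10 screening threshold (planned type I error 4.9%).

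**The case against.** The strongest reply is that little is at risk. The pre-test score of the same outcome, taken about a week earlier, is already in every model, and nothing in the documents places R² near 5–10%. At 0–2% there is no useful gain. For parent outcomes the factors describe the adolescent, so the gain may be nil. All of this stands, and it is why the point is minor.

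Second, 1:1 stratified allocation from several sequences points towards Case A, where the estimate loses no precision. That also stands as a reading. But separate sequences drawn without blocks impose no balance, and the protocol does not say which was meant. Power is lost in both cases: through a conservative test in one, a noisier estimate in the other.

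Third, selection by baseline test showed no inflated type I error. True at the two thresholds simulated, 0.05 and 0.10; others are untested, since the SAP names none. The case for dropping the selection is that it ignores prognostic value and leaves the model unspecified.

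Fourth, in Case B at R² 10% the planned SE is not quite right: an SE ratio of 1.046 against an SD ratio of 1.033 means it is about 1% wide. Correct, and too small to change the conclusion.

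Fifth, the moderator analyses would normally carry gender and health status as main effects. They are additional analyses and leave out race/ethnicity.

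**Conclusion.** The concern holds and is minor. As written, the main models do not fix the stratification factors as covariates, and the baseline-test rule will almost never bring them in if assignment is blocked.

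For R² of 5–10% the loss is about 1.5 to 3 power points at N = 200. With balanced strata it appears as an SE 2.6–5.4% too wide; without blocks, as an estimate about 2–3% less precise, worth about 7–13 pairs. At R² near zero there is no loss. Omitting the factors is not claimed to bias the treatment effect.

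Confidence in the size is medium, because N, the correlation, R² and the threshold are all assumed. The figures apply to continuous outcomes in linear regression. The SAP also allows skewed variables to be transformed or categorised, and categorised outcomes were not examined.

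**What to change.** Replace the covariate sentence in Main analyses with:

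> Every outcome model will include condition, the pre-test score of that outcome, and the randomisation stratification factors (gender, race/ethnicity, health status, as recorded in the screener) as main effects. If an arm has no non-binary adolescent, that level will be combined, for adjustment only, with one other gender level named before outcome data are seen; no pair will be excluded. Baseline characteristics will be described by arm, and no covariate will be added or dropped because of baseline significance tests.

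If age is wanted as a covariate, name it in the same sentence. State in Design whether assignment within strata is blocked.

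The merge rule is meant to act rarely. At N = 200 with 3% non-binary it triggers in 9–10% of trials without blocks and 6–7% with blocks of 4 (38–40% at N = 100 without blocks). A threshold of fewer than five would trigger in 92–97% at N = 200. Merging into boy or girl gave the same SE.

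The cost is SAP wording only; the data are already collected at screening. Each model spends four degrees of freedom (2 + 1 + 1), or three if levels are merged. If the factors are not prognostic, precision at N = 200 is about 0.5–0.7% worse without blocks and under 0.2% different with blocks. The SE is 0.8% wider at N = 100 and 0.3% at N = 400, without blocks.
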